11. STATISTICAL CONSIDERATIONS

11.1 Sample Size

Ir vs IrCs comparison

A non-inferiority design is proposed, based upon the proportion of patients progression-free at 12 weeks from randomisation. In a previous study in a similar patient population receiving irinotecan, median PFS was 4.2 months, with 63.3% of patients progression-free at 12 weeks.³⁸ There are no previous best supportive care (BSC) trials that have included regular CT scan assessments, however in a trial comparing irinotecan with BSC, at the time point that 63% of Ir

patients were alive, less than 40% of BSC patients were alive⁴⁰. On this basis we have estimated that a similar proportion – 40% - of patients on BSC would be expected to be progression-free at 12 weeks applying standard WHO or RECIST criteria. On this basis irinotecan contributes at least 23% to the proportion of patients progression-free at 12 weeks. On the basis of clinician consensus IrCs will be defined as no worse than Ir if median PFS is at least 3 months with IrCs, equivalent to at least 52.7% of patients in the IrCs arm progression-free at 12 weeks. This corresponds to a reduction of no more than 10.6% in the proportion of patients progression-free at 12 weeks which is our non-inferiority margin; retaining more than half the effect that irinotecan has over BSC. The sample size calculation for the Ir vs. IrCs comparison remains the same since there is no data to suggest that *K-RAS* status is a predictive factor for Irinotecan or Ciclosporin.

We will conduct a one-sided test for non-inferiority.³⁹ With 80% power and a significance level of 2.5%, 680 patients are required to test for this degree of non-inferiority using a one-sided chi-squared test without continuity correction. To account for a 10% drop-out or 5% cross-over, 750 patients (375 per arm) would need to be randomised in total. This sample size also gives over 90% power for claiming non-inferiority of PFS using a one-sided modified log-rank test with significance level 2.5% (at least 273 PFS events are required to assess non-inferiority with 80% power), and allows detection of a clinically relevant relative reduction of 50% (from 20% with Ir to 10% with IrCs) in the proportion of patients experiencing grade 3+ diarrhoea within 12 weeks of randomisation, with over 90% power and at a 5% (two-sided) significance level, using a two-sided chi-squared test without continuity correction.

Although not primarily designed to detect superior efficacy for IrCs compared with Ir, this is a possible consequence of reduced toxicity if it leads to improved treatment duration. The proposed sample size will provide 80% power to detect an increase in median PFS of 1.1 months, or an increase in OS of 2.9 months with Cs, using a 2-sided log-rank test at the 5% significance level.

Ir vs IrPan comparison (patients with wild-type *K-RAS* status not previously receiving an anti-EGFR targeted therapy)

For the +/- panitumumab comparison, a superiority design is proposed, based upon overall survival (OS). Previous literature has found median OS for patients taking Ir to be between 9.2 and 10.8 months, mostly in patients pre-treated with only FU/LV.^{38,40} Since many PICCOLO patients will have received FU/LV and oxaliplatin, we have assumed a slightly shorter median OS of 9 months in the control arm.

Since this comparison considers patients with wild-type *K-RAS* status only, for whom we expect the benefit of the addition of panitumumab to irinotecan to be increased, the study is now powered to detect a reduction in hazard rate of 30% with the addition of panitumumab, compared to no panitumumab. With 80% power and a significance level of 5%, 466 patients (246 deaths) are required to test for this degree of superiority using a 2-sided log-rank test, assuming patients are followed for a fixed length of time and that the hazard ratio is constant. 480 patients (240 per arm) will therefore be recruited to allow for loss to follow-up.

Previous anti-EGFR targeted therapy use

We expect that approximately 15% of patients recruited to PICCOLO will have previously been treated with an anti-EGFR targeted therapy. It is possible that there will be cross-resistance between anti-EGFR targeted therapies and other EGFR agents including panitumumab, and it is therefore important that the Ir vs. IrPan comparison compares only patients who have not

previously received anti-EGFR targeted therapies. This comparison will therefore include all patients who have not previously received an anti-EGFR targeted therapy who have been randomised to receive either Ir or IrPan (and who have wild-type *K-RAS* status).

Since previous anti-EGFR targeted therapy use is of no concern for the Ir vs. IrCs comparison, this analysis will include all patients randomised to receive either Ir or IrCs under Protocol Version 1.0, and all patients randomised to receive either Ir or IrCs via the Ir vs. IrCs randomisation in this amended protocol, regardless whether or not they have previously used anti-EGFR targeted therapy.

The two primary comparisons of Ir vs. IrCs and Ir vs. IrPan are essentially two independent comparisons⁴¹. We therefore aim to recruit 480 patients who have wild-type *K-RAS* status and who have not previously received an anti-EGFR targeted therapy (240 patients per arm) to the Ir vs. IrPan comparison. However, dependent upon the proportion of patients with unknown *K-RAS* status, there may be some over-recruitment to this comparison. We expect approximately 15% of all patients recruited to this comparison to have previously received an anti-EGFR targeted therapy therefore the expected sample size for the exploratory analysis of Ir vs. IrPan for those patients previously receiving an anti-EGFR targeted therapy (and who have wild-type *K-RAS* status) is approximately 86 patients (43 patients per arm of Ir/IrPan).

K-RAS status

We expect that the split between mutant *K-RAS* status and wild-type *K-RAS* status will be approximately 42:58, and that approximately 15% of patients will have unknown *K-RAS* status. The proportion of patients with unknown status will be monitored as this figure may vary. Only patients with wild-type *K-RAS* status will be randomised to the Ir vs. IrPan comparison. There will, however, be some patients randomised to IrPan via protocol Version 1.0 who will have either mutant or unknown *K-RAS* status. We anticipate that approximately 167 mutant or unknown *K-RAS* status patients will have been randomised to receive either Ir or IrPan under Protocol Version 1.0, of whom approximately 19 will have previously received an anti-EGFR targeted therapy. An exploratory analysis will be carried out on these patients.

Recruitment to both comparisons should continue until there are a total of at least 750 patients in the Ir versus IrCs comparison, and at least 480 wild-type *K-RAS* status, non-anti-EGFR pre-treated patients in the Ir versus IrPan comparison. The recruitment ratio to the Ir vs. IrCs comparison and the Ir vs. IrPan comparison will vary according to the proportion of patients with unknown *K-RAS* status, which we anticipate to be approximately 15%. Based on these assumptions, we expect the recruitment ratio to the Ir vs. IrCs comparison and the Ir vs. IrPan comparison to be approximately 50.7:49.3.

The total expected sample size, having already recruited 494 patients via Protocol Version 1.0, is therefore anticipated to be approximately **1324**, assuming 15% of patients have unknown *K-RAS* status at the time of randomisation, and assuming 15% of patients have previously received anti-EGFR targeted therapy.

The proportion of patients randomised with unknown *K-RAS* status, and the proportion of patients previously receiving anti-EGFR therapy, will be monitored in order to ensure that the assumptions made remain valid.

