Analysis will be based on the lower limit of the 95% confidence interval (CI) (one-sided type I error rate of 2.5%) of the difference in proportion of patients progression free at 12 weeks from randomisation between each treatment group. Logistic regression will also be used to adjust for the minimisation factors, previous anti-EGFR targeted therapy use and any other covariates identified to influence patients' prognosis. Treatment and covariate estimates with corresponding 95% CIs will be given. To account for any deaths from causes other than colorectal cancer which may occur within 12 weeks of randomisation, for whom no evidence of disease progression was found, sensitivity analyses will be conducted classifying these patients as progression-free (these patients will be classed as having progressive disease at 12 weeks in the main analysis). Sensitivity analysis will also be conducted to account for patients with missing data regarding progression at 12 weeks, using the local assessment or classifying these patients as with progressive disease, as appropriate. The primary analysis will be based on the lower limit of the confidence interval of the odds ratio for the proportion of patients progression free at 12 weeks, obtained using logistic regression which adjusts for the minimisation factors.

Secondary Endpoints

The difference in proportion of patients who are free from treatment failure, defined as clinical or radiological progression, death due to colorectal cancer or toxicity, or termination of treatment irrevocably, at 12 weeks from randomisation between treatment groups will be compared using a two-sided chi-squared test. Logistic regression will also be used to adjust for the minimisation factors, previous anti-EGFR targeted therapy use and any other covariates identified to influence patients' prognosis. Treatment and covariate estimates with corresponding 95% CIs will be given. Sensitivity analyses will be conducted to allow for any deaths from causes other than colorectal cancer within 12 weeks of randomisation. Sensitivity analysis will also be conducted to account for patients with missing data regarding treatment failure at 12 weeks, classifying these patients as with treatment failure.

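### The IrCs non-inferiority margin and sample size are set on a difference in proportions, but section 12 also names an adjusted odds ratio as the primary analysis, for which the Protocol gives no margin and no power

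*Protocol*

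**What the plan says.** Protocol section 11.1 (Sample Size, Ir vs IrCs comparison) builds the design on two proportions:

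- Control: "median PFS was 4.2 months, with 63.3% of patients progression-free at 12 weeks".
- Lowest acceptable result with IrCs: "equivalent to at least 52.7% of patients in the IrCs arm progression-free at 12 weeks".
- Margin: "This corresponds to a reduction of no more than 10.6% in the proportion of patients progression-free at 12 weeks which is our non-inferiority margin".
- Size: "With 80% power and a significance level of 2.5%, 680 patients are required to test for this degree of non-inferiority". The test named for this is a chi-squared comparison of the two proportions, one-sided and uncorrected for continuity.
- Allowance for losses: "To account for a 10% drop-out or 5% cross-over, 750 patients (375 per arm) would need to be randomised in total".

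Section 12 (Ir vs IrCs comparison, Primary Endpoint) opens by basing the analysis on the lower 95% confidence limit for the difference between arms in the proportion progression-free at 12 weeks. The same paragraph ends differently: "The primary analysis will be based on the lower limit of the confidence interval of the odds ratio", obtained from logistic regression adjusted for the minimisation factors.

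Three other rules in section 12 bear on how many patients are analysed. The 12-week analysis takes patients assessed between 10 and 14 weeks. A living patient without a central review is counted as progression-free in the primary analysis. The per-protocol analysis has equal weight with intention-to-treat for non-inferiority.

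**The concern.** A non-inferiority conclusion depends on comparing a confidence limit with a margin fixed in advance. Here the margin exists on one scale and the analysis named primary is on another, so the Protocol gives no threshold for that odds-ratio limit. The two scales are not interchangeable. An odds ratio that matches 10.6 points at one control rate corresponds to a different number of points at another, so the same data could pass on one scale and fail on the other. If the scale or the converted margin were settled after the data were seen, the verdict would be open to challenge.

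The 80% power is affected too, because it was calculated for a chi-squared comparison of proportions and not for the odds-ratio analysis.

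**Working it through.** **Inputs (section 11.1).** Control 63.3%; lowest acceptable 52.7%; margin 10.6 points; one-sided 2.5%; power 80%; 680 patients before and 750 after the allowance; 1:1 allocation. z-values 1.960 and 0.8416, sum 2.8016, squared 7.849. p(1−p) at 63.3% is 0.2323.

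**1. Reproducing 680.** Comparison of 63.3% with 52.7%, pooled variance under the null, mean proportion 0.58:

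n per arm = [1.960 × √(2 × 0.58 × 0.42) + 0.8416 × √(0.633 × 0.367 + 0.527 × 0.473)]² / 0.106² = (1.368 + 0.584)² / 0.01124 ≈ 339.2, rounded up to 340, or **680 in total**. The stated figure reproduces exactly for the test named.

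**2. Non-inferiority on the difference, both arms truly at 63.3%.**

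n per arm = 2 × 0.2323 × 7.849 / 0.106² ≈ 324.6, rounded up to 325, or 650 in total. On this formula 680 is slightly generous.

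**3. Allowance for losses.** 750 × 0.9 = 675, against 680. Exact inflation is 680 / 0.9 = 755.6, or 756. Power at 675 evaluable:

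- Protocol's own formula: 79.8%
- Equal-rates non-inferiority formula: 0.106 / √(2 × 0.2323 / 337.5) − 1.960 = 0.897, so 81.5%

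**4. Odds-ratio scale.** The Protocol gives no margin here. *Assumption:* convert its own proportions, (0.527/0.473) / (0.633/0.367) = 0.646, with log −0.437. Unadjusted Wald test, both arms truly at 63.3%:

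n per arm = 2 × 7.849 / (0.2323 × 0.437²) ≈ 353.8, rounded up to 354, or **708 evaluable** (787 randomised if 10% are lost).

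Power = Φ(0.437 / √(2 / (n × 0.2323)) − 1.960), with n per arm:

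| Evaluable | Odds ratio, margin 0.646 | Difference, equal rates | Protocol's formula |
|---|---|---|---|
| 675 | 78.1% | 81.5% | 79.8% |
| 680 | 78.4% | 81.8% | 80.1% |
| 750 | 82.2% | 85.3% | 83.8% |

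Simulation of the unadjusted odds-ratio test agrees: about 78% at 674 to 676 and 82.0% at 750. Taking the true rate from 60% to 65%, with the margin held at 0.646 or re-converted from 10.6 points, gives 77.3% to 79.4% at 675 and 81.4% to 83.4% at 750. Power stays at or above 80% until losses exceed 1 − 708/750 = 5.6%.

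**5. The scales diverge away from 63.3%.** What an odds ratio of 0.646 means in points:

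- Control 60%: odds 1.5 × 0.646 = 0.969, or 49.2%; 10.8 points
- Control 70%: odds 2.333 × 0.646 = 1.507, or 60.1%; 9.9 points
- Control 75%: odds 3 × 0.646 = 1.938, or 66.0%; 9.0 points

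At a 75% control rate, a deficit of 9.5 points lies inside 10.6 points. Its odds ratio is (0.655/0.345) / 3 = 0.633, which lies beyond 0.646.

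**The case against.** The defence has several good points.

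- **The stated claim is correct as stated.** 680 and 80% reproduce for the chi-squared test named, and section 11.1 claims no power for an odds-ratio analysis. A reader might infer that the true power is 78%, not 80%. The documents do not support that: 78% belongs to a different test, with a margin the Protocol never states and a full 10% loss.
- **The drop-out shortfall is rounding.** A reader might infer that 750 is materially too few. It is 6 below 756 and costs about 0.2 points of power. Section 11.1 also sets recruitment at no fewer than 750.
- **The full loss may not occur.** Section 12 keeps living patients without a central review in the primary analysis, and counts deaths without observed progression as progressive disease. The 10-to-14-week assessment window could still remove some patients; the Protocol does not say how many.
- **Removing both allowances goes too far.** Taking off 10% drop-out and 5% cross-over together leaves 641 evaluable (750 × 0.9 × 0.95) and 76.0% on the odds ratio. Section 11.1 offers the two as alternatives, and cross-overs stay in the intention-to-treat set. At most this describes a per-protocol scenario.
- **The difference in proportions is also to be analysed.** It would be wrong to say that the trial will not run the comparison it was sized for.
- **An odds-ratio margin may be in the statistical analysis plan**, which was not available.

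What remains is that the Protocol itself gives two bases for the primary analysis and ties its only margin and its sample size to one of them. A margin held in the analysis plan would supply the threshold, but would not reconcile section 12 or make the 80% apply to the odds ratio.

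**Conclusion.** The point holds as an inconsistency of scale. Section 12 gives two bases for the primary IrCs analysis. The 10.6-point margin and the 680/750 sample size belong to the difference in proportions, so within the Protocol the odds-ratio analysis named primary has no stated margin and no calculated power.

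The effect on power is small and conditional: about 78% to 82% on the odds ratio, depending on whether 675 or 750 patients are analysed. This rests on the converted margin of 0.646, true equality at 63.3% and an unadjusted Wald approximation. The planned analysis is covariate-adjusted, and an adjusted odds ratio is not the same quantity as one computed from the two raw proportions, so these figures are a guide only.

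The larger consequence is for the non-inferiority verdict, since the two margins coincide only at a control rate of 63.3%.

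**What to change.** In section 12, name one primary scale for the IrCs comparison.

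- **Preferred:** the difference in proportions, tested against 10.6 points (covariate-adjusted if wished), with the odds ratio as supportive. Sections 11.1 and 12 then agree. Power at 675 evaluable can be quoted as about 81.5% by the equal-rates non-inferiority formula, or 79.8% by the formula behind 680.
- **Alternative:** keep the adjusted odds ratio as primary, state its margin in advance (0.646 if converted from 63.3% and 52.7%), and restate the power as about 78% to 82% depending on losses.

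As a minor correction in section 11.1, say that 750 leaves 675 evaluable after 10% drop-out, the exact inflation of 680 being 756.

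The cost is wording only, with no extra patients. If the odds ratio is kept, the quoted power becomes slightly less favourable at the lower end.

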11.2 Planned Recruitment Rate

Target recruitment is 3 years. A total of 494 patients have been recruited under Protocol Version 1.0, therefore approximately 830 patients are still to be recruited in order to achieve the required sample size: an average of 46 per month (with 18 months recruitment remaining). Given that accrual to FOCUS was 60-65 patients per month, we feel this goal is realistic. Patients in the ongoing FOCUS2 trial (460 patients) may be eligible for PICCOLO after progression, as will patients in COIN (2400 patients). Recruitment will stop when 480 patients who have not previously received an anti-EGFR targeted therapy and who have wild-type *K-RAS* status have been recruited to the Ir vs. IrPan comparison, and when 750 patients have been recruited to the Ir vs. IrCs comparison.

12. STATISTICAL ANALYSIS

Statistical analysis is the responsibility of the CTRU Statistician. A final statistical analysis plan corresponding to Protocol Version 1.0 has been written in accordance with current CTRU standard operating procedures and has been finalised and agreed by the following people: the trial statistician and supervising statistician, the project manager and the Chief Investigator. Changes to this finalised analysis plan, and reasons for changes, will be documented. The above people will remain blinded to the data and will not have access to the complete CRFs.

All analyses will be conducted on the intention-to-treat (ITT) population (as defined in the statistical analysis plan), where patients will be included according to the treatment they were randomised to, and the per-protocol population (if necessary), where patients will be included according to the treatment they received. Patients defined as major protocol violators will be excluded from the per-protocol analysis. Major protocol violators were defined prior to the start of recruitment and any subsequent changes, and reasons for changes, will be documented. For the superiority endpoints the ITT analysis will be given primacy, however for the non-inferiority endpoints equal weighting will be given to both the ITT analysis and the per-protocol analysis, as the ITT is likely to be the least conservative approach when testing for non-inferiority. The safety population will consist of all patients who receive at least one dose of study treatment, and will be considered as necessary.

Overall survival is defined as the time from date of randomisation to date of death from any cause; patients with missing follow-up data, or who are still alive at the time of analysis, will be censored at the last date they were known to be alive. Progression-free survival is defined as the time between date of randomisation and date of disease progression or death from any cause. Patients with missing follow-up data, or who are alive and progression-free at the time of analysis, will be censored at the date they were last known to be alive and progression-free.

Analysis of 12-week assessments will include all patients assessed between 10 and 14 weeks from randomisation. A sensitivity analysis will be conducted to allow for patients assessed outside of this 2 week time frame. Analysis of response will be performed using the centrally reviewed outcome. If the centrally reviewed outcome is missing, the primary analysis will class the patient as being progression-free at 12 weeks (if alive), and a sensitivity analysis will be conducted using the outcome of the local assessment. If this is also missing, the patient will be classed as having progressed at 12 weeks in the sensitivity analysis.

A two-sided 5% significance level will be used for all superiority endpoints, and a one-sided 2.5% significance level will be used for all non-inferiority endpoints.

Safety data (adverse events and serious adverse events as detailed in Section 8) will be presented for all patients by treatment group and comparison, and by relationship to study drug, or underlying colorectal cancer.

Ir vs IrCs comparison

All patients randomised to receive either Ir or IrCs via protocol Version 1.0 or to the Ir vs. IrCs comparison under protocol Version 2.0 (i.e. mutant/unknown *K-RAS* status), regardless of previous anti-EGFR targeted therapy use, will be included in this comparison.

Primary Endpoint

Analysis will be based on the lower limit of the 95% confidence interval (CI) (one-sided type I error rate of 2.5%) of the difference in proportion of patients progression free at 12 weeks from randomisation between each treatment group. Logistic regression will also be used to adjust for the minimisation factors, previous anti-EGFR targeted therapy use and any other covariates identified to influence patients' prognosis. Treatment and covariate estimates with corresponding 95% CIs will be given. To account for any deaths from causes other than colorectal cancer which may occur within 12 weeks of randomisation, for whom no evidence of disease progression was found, sensitivity analyses will be conducted classifying these patients as progression-free (these patients will be classed as having progressive disease at 12 weeks in the main analysis). Sensitivity analysis will also be conducted to account for patients with missing data regarding progression at 12 weeks, using the local assessment or classifying these patients as with progressive disease, as appropriate. The primary analysis will be based on the lower limit of the confidence interval of the odds ratio for the proportion of patients progression free at 12 weeks, obtained using logistic regression which adjusts for the minimisation factors.

Secondary Endpoints

The difference in proportion of patients who are free from treatment failure, defined as clinical or radiological progression, death due to colorectal cancer or toxicity, or termination of treatment irrevocably, at 12 weeks from randomisation between treatment groups will be compared using a two-sided chi-squared test. Logistic regression will also be used to adjust for the minimisation factors, previous anti-EGFR targeted therapy use and any other covariates identified to influence patients' prognosis. Treatment and covariate estimates with corresponding 95% CIs will be given. Sensitivity analyses will be conducted to allow for any deaths from causes other than colorectal cancer within 12 weeks of randomisation. Sensitivity analysis will also be conducted to account for patients with missing data regarding treatment failure at 12 weeks, classifying these patients as with treatment failure.

Kaplan Meier curves for overall survival and progression-free survival will be calculated, and differences between the treatment groups compared using one-sided modified log-rank tests. Survival will also be compared using multivariate modelling, Cox's Proportional Hazards model if appropriate, to adjust for the minimisation factors, previous anti-EGFR targeted therapy use and other important prognostic factors. HRs and corresponding 95% CIs will be presented. Sensitivity analysis will be considered to account for missing data for PFS analysis.

Patients' best response rate⁴² will be assessed by calculating the 95% CI of the difference in response rates between the two treatment groups. In addition, a one-sided chi-squared test for trend (or appropriate version) and logistic regression, to adjust for the minimisation factors,

previous anti-EGFR targeted therapy use and other prognostic factors, will be performed. Sensitivity analyses will be conducted to allow for any deaths from causes other than colorectal cancer, for whom no response status was observed.

Quality of life will be summarised using adjusted for baseline mean scores and 95% CIs for each EORTC QLQ-C30 domain, obtained from a multi-level repeated measures model, assuming missing data at random. Missing data patterns will be examined carefully, and if missing data patterns suggest data are missing not at random, analyses will also be carried out using pattern-mixture models, and data summarised using the Standardised Area Under the Curve. The MRC treatment value/acceptability supplement will be summarised descriptively with bar charts and summary tables for each question. The mean adjusted for baseline total Dermatology Life Quality Index score and scores for each domain will be presented with corresponding 95% confidence intervals.

To assess toxicity, the maximum grade per patient, rate per cycle and all cause mortality within 60 days of randomisation will be summarised descriptively for each treatment group. The difference between the two treatment groups in proportion of patients experiencing grade 3+ diarrhoea within 12 weeks of randomisation will be tested using a two-sided chi-squared test without continuity correction (or appropriate version), and 95% CI's will be presented. Logistic regression will also be used to adjust for the minimisation factors, previous anti-EGFR targeted therapy use and any other prognostic factors. Reasons for stopped treatment will be summarised.

Should non-inferiority of IrCs to Ir be shown, we will consider both treatment groups together, and conduct exploratory subgroup analyses comparing patients' outcome according to the clinical minimisation factors and previous anti-EGFR targeted therapy use.

Ir vs IrPan comparison (patients with wild-type K-RAS status not previously receiving an anti-EGFR targeted therapy)

Patients with wild-type *K-RAS* status randomised via the 'no previous anti-EGFR targeted therapy use' randomisation will be included in this comparison.

Primary Endpoint

Overall survival curves will be calculated using the Kaplan Meier method and compared using a 2-sided log-rank test. OS will also be compared between the control and experimental groups using multivariate modelling. Cox's proportional hazards model, if appropriate, will be used to adjust for the minimisation factors and other important prognostic factors. HRs and corresponding 95% CIs for OS will be presented. Primary analysis will be based on the multivariate analysis which adjusts for the minimisation factors.

Secondary Endpoints

The difference in proportion of patients who are progression-free at 12 weeks from randomisation between treatment groups will be compared using a two-sided chi-squared test. Logistic regression will also be used to adjust for the minimisation factors and any other covariates identified to influence patients' prognosis. Treatment and covariate estimates with corresponding 95% CIs will be given. To account for any deaths from causes other than colorectal cancer which may occur within 12 weeks of randomisation, for patients who have no evidence of disease progression, sensitivity analyses will be conducted classifying these patients as progression-free (these patients will be classed as with progressive disease at 12

weeks in the main analysis). Sensitivity analysis will also be conducted to account for patients with missing data regarding progression at 12 weeks, using local assessment data or classifying these patients as with progressive disease, as appropriate.

Kaplan Meier curves for progression-free survival will be calculated, and the difference between the treatment groups compared using a two-sided log-rank test. Survival will also be compared using multivariate modelling, Cox's Proportional Hazards model if appropriate, to adjust for the minimisation factors and other important prognostic factors. HRs and corresponding 95% CIs will be presented. Sensitivity analysis will be considered to account for missing data for PFS analysis.

Patients' best response rate⁴² will be assessed by calculating the 95% CI of the difference in response rates between the two treatment groups. In addition, a two-sided chi-squared test for trend (or appropriate version) and logistic regression, to adjust for the minimisation factors and other prognostic factors will be performed. Sensitivity analyses will be conducted to allow for any deaths from causes other than colorectal cancer.

Quality of life will be summarised using adjusted for baseline mean scores and 95% CIs for each EORTC QLQ-C30 domain, obtained from a multi-level repeated measures model, assuming data to be missing at random. Missing data patterns will be examined carefully, and if missing data patterns suggest data are missing not at random, analyses will also be carried out using pattern-mixture models, and data summarised using the Standardised Area Under the Curve. The MRC treatment value/acceptability supplement will be summarised descriptively with bar charts and summary tables for each question. The mean adjusted for baseline total Dermatology Life Quality Index score and scores for each domain will be presented with corresponding 95% confidence intervals.

To assess toxicity, the maximum grade per patient, rate per cycle and all cause mortality within 60 days of randomisation will be summarised descriptively for each treatment group. Reasons for stopped treatment will be summarised.

It is possible that the presence of skin rash may be associated with the clinical effectiveness of anti-EGFr therapies⁴³. For exploratory purposes it is therefore planned to examine the possibility that the treatment effect, as measured by best response rate, differs according to grade of acneiform rash. Best response rate will be assessed using ordered logistic regression adjusting for treatment, grade of skin toxicity and their interaction.

Ir vs. IrPan comparison (patients with wild-type K-RAS status previously receiving anti-EGFR targeted therapies)

Exploratory Analysis

The proportion of patients progression-free at 12 weeks from randomisation will be summarised for both the Ir and IrPan arms. 95% confidence intervals will also be reported.

To assess toxicity, the maximum grade per patient, rate per cycle and all cause mortality within 60 days of randomisation will be summarised descriptively for each treatment group. Reasons for stopped treatment will be summarised.

Ir vs. IrPan comparison (patients randomised to receive Ir or IrPan under Protocol Version 1.0 who have mutant or unknown K-RAS status, regardless of previous anti-EGFR targeted therapy)

Exploratory Analysis

The proportion of patients progression-free at 12 weeks from randomisation will be summarised for both the Ir and IrPan arms. 95% confidence intervals will also be reported.

To assess toxicity, the maximum grade per patient, rate per cycle and all cause mortality within 60 days of randomisation will be summarised descriptively for each treatment group. Reasons for stopped treatment will be summarised.

